14.3 Appendix 3: baseline and follow-up questionnaires

BASELINE QUESTIONNAIRE

SOCIODEMOGRAFIC

Nationality:

- a) Italian
- b) Other, please specify _____

Education

- Elementary
- Lower middle
- Higher middle
- Degree
- Other

Marital status

- Single
- Married or living together
- Separated or divorced
- Widowed

Employment status

- Paid work (full or part time)
- No paid work (retired, housewife, other)

Do you use internet to search for health information?

- Never
- A few times a month
- At least once a week

- Several times a week
- Daily

Have you already had a mammography?

- Yes, in a public facility, when? _____(year)
- Yes, in a private facility, when? _____(year)
- No

Has anyone in your family or your friends had breast cancer?

- Yes
- No

Have you ever had a tumor?

- Yes If Yes, type of tumor _____
- No

Have you participated in other organized screening programs?

Fecal occult blood tests for colorectal cancer	 Yes  No
Pap test for cervical cancer	 Yes  No

PERCEIVED RISK

Perceived risk of breast cancer relative to the average woman

Much lower	A bit lower	About the same	A bit higher	Much higher
------------	-------------	----------------	--------------	-------------

KNOWLEDGE

What is a SCREENING mammogram?

- A mammogram you have when you're healthy
- A mammogram you have if you notice a change or lump in your breast

An organized mammography screening program can detect a breast cancer in an early stage and lead to less invasive surgery and treatment

True

False

Which of the following statements about mammography reflects your opinion?

Regular mammography every two years in women who are well:

Prevents the risk of breast cancer

Does not prevent the risk of breast cancer

Who do you think is more likely to die from breast cancer?

Women who have screening mammograms

Women who do not have screening mammograms

Do you think a screening mammogram will find every breast cancer?

Yes

No

Do all women with an abnormal screening mammogram result have breast cancer?

Yes

No

Which of these 2 statements best describes over-detection?

Screening finds a cancer that would never have caused trouble

Screening finds an abnormality but extra tests show it is not cancer

Screening leads some women with a harmless cancer to get treatment they do not need.

True

False

In the organized mammography screening program, the presence of two expert radiologists increases the ability to identify a breast tumor

- True
- False

The usefulness of an organized mammography screening program is:

- Totally recognized by doctors and researchers
- Questioned by some doctors and researchers

For the next few questions, I would like you to imagine 1000 ordinary women who are 50 years old who have participated regularly in organized mammography screening program for 30 years

How many women do you think will avoid dying from breast cancer because of screening?

- 8
- 50
- 150

How many women do you think will be diagnosed and treated for a breast cancer that is not harmful?

- 4
- 25
- 70

Now, I would like you to imagine 1000 ordinary women who are 50 years old who have not participated in organized mammography screening program, in their next 30 years.... How many die of breast cancer?

- 20
- 80
- 140

ATTITUDE

For you, having breast screening is.....

A bad thing	Not a bad thing
1 2 3 4 5	
Beneficial	Not beneficial
1 2 3 4 5	
Harmful	Not harmful
1 2 3 4 5	
A good thing	Not a good thing
1 2 3 4 5	
Worthwhile	Not worthwhile
1 2 3 4 5	
Important	Unimportant
1 2 3 4 5	

INTENTION

Intending to be screened

Definitely will	Likely to	Unsure	Not likely to	Definitely will not
-----------------	-----------	--------	---------------	---------------------

FOLLOW-UP QUESTIONNAIRE

ATTITUDE

For you, having breast screening is.....

A bad thing

Not a bad thing

1 2 3 4 5

Beneficial

Not beneficial

1 2 3 4 5

Harmful

Not harmful

1 2 3 4 5

A good thing

Not a good thing

1 2 3 4 5

Worthwhile

Not worthwhile

1 2 3 4 5

Important

Unimportant

1 2 3 4 5

SATISFACTION/ACCEPTABILITY OF THE INFORMATION

Thinking back to the type of information material you have read ...			
Was there enough information?	Too much	Too little	Fair
Was the information on benefit new to you?	All or almost all	Some	None
Was the information on harm new to	All or almost all	Some	None

you?			
Was the information clear?	All or almost all	Some	None
The information seemed...	In favor of screening	Balanced	Against screening
Did it help you to decide?	Yes	Not much	No
Would you recommend it to other women?	Yes	Not much	No
Only for Decision-Aid	All or almost all	Some	None
Was the controversy new to you?			

DECISIONAL CONFLICT (SURE QUESTIONNAIRE)

Sure of myself

Do you feel SURE about the best choice for you?

Yes
 No

Understanding information

Do you know the benefits and risks of each option?

Yes
 No

Risk-benefit ratio

Are you clear about which benefits and risks matter most to you?

Yes
 No

Encouragement

Do you have enough support and advice to make a choice?

Yes
 No

INTENTION

Intending to be screened

Definitely will	Likely to	Unsure	Not likely to	Definitely will not
-----------------	-----------	--------	---------------	---------------------

KNOWLEDGE

What is a SCREENING mammogram?

- A mammogram you have when you're healthy
- A mammogram you have if you notice a change or lump in your breast

An organized mammography screening program can detect a breast cancer in an early stage and lead to less invasive surgery and treatment

- True
- False

Which of the following statements about mammography reflects your opinion?

Regular mammography every two years in women who are well:

- Prevents the risk of breast cancer
- Does not prevent the risk of breast cancer

Who do you think is more likely to die from breast cancer?

- Women who have screening mammograms
- Women who do not have screening mammograms

Do you think a screening mammogram will find every breast cancer?

- Yes
- No

Do all women with an abnormal screening mammogram result have breast cancer?

- Yes
- No

Which of these 2 statements best describes over-detection?

- Screening finds a cancer that would never have caused trouble
- Screening finds an abnormality but extra tests show it is not cancer

Screening leads some women with a harmless cancer to get treatment they do not need.

- True
- False

In the organized mammography screening program, the presence of two expert radiologists increases the ability to identify a breast tumor

- True
- False

The usefulness of an organized mammography screening program is:

- Totally recognized by doctors and researchers
- Questioned by some doctors and researchers

For the next few questions, I would like you to imagine 1000 ordinary women who are 50 years old who have participated regularly in organized mammography screening program for 30 years

How many women do you think will avoid dying from breast cancer because of screening?

- 8
- 50
- 150

How many women do you think will be diagnosed and treated for a breast cancer that is not harmful?

- 4
- 25

70

Now, I would like you to imagine 1000 ordinary women who are 50 years old who have not participated in organized mammography screening program, in their next 30 years.... How many die of breast cancer?

20

80

140

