5.1 Primary endpoints

Informed choice will be measured according to the three-dimensional framework of Marteau et al. (26), which covers knowledge, attitude and intention. The statistical hypothesis for the primary

endpoint is of superiority, the study is designed to detect a 10% difference between the control and the intervention group, according to the literature available (22, 27).

Knowledge will be measured using a questionnaire developed on the basis of literature (22, 27). It will be structured in thirteen questions with multiple choice answers, with two to three options. Ten questions will be qualitative and 3 will be numerical. The score and threshold to reach an “adequate knowledge” were decided *a priori*, following the approach described in the literature (22, 27). Each correct answer will receive one point. The maximum total score is 13 out of 13. A score of 8 out of 13 (about 60%) or higher would be considered “adequate knowledge”.

Attitude will be measured through a scale used in the literature available (22, 27), consisting of six items with five response options from 1 to 5, with a total score from 6 to 30. For informed choice, we set the threshold for a positive attitude at 24 and consequently the score <24 point a negative attitude.

Intention to be screened will be measured using one item with five responses: Definitely will, Likely to, Unsure, Not likely to, Definitely will not. For informed choice, we classified “definitely will” and “likely to” as positive intentions. This item will be collected at the end of the information session on the web and in the follow-up questionnaire. In case of no consistency between the two answers, the answer in the follow-up questionnaire will be considered as conclusive.

The informed choice will be assessed as a dichotomous outcome. A woman will be considered as able to express an informed choice if she has adequate knowledge and her attitudes and intentions are consistent (both positive or both negative) in the follow-up questionnaire.

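### The printed follow-up questionnaire shows the decision-aid arm alone an item that presupposes a controversy, before intention and knowledge are measured, and this can cue one of the 13 scored knowledge answers.

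*Combined protocol and SAP*

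**What the plan says.** Section 5.1 scores the primary endpoint at follow-up. A woman makes an informed choice "if she has adequate knowledge and her attitudes and intentions are consistent (both positive or both negative) in the follow-up questionnaire". For knowledge, "Each correct answer will receive one point". "A score of 8 out of 13 (about 60%) or higher would be considered" adequate. Intention is asked twice, at the end of the web session and at follow-up. If the two differ, "the answer in the follow-up questionnaire will be considered as conclusive".

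The follow-up form in section 14.3 (Appendix 3) is printed in this order: attitude, "SATISFACTION/ACCEPTABILITY OF THE INFORMATION", decisional conflict (SURE), intention, knowledge. The eighth and last satisfaction row is marked "Only for Decision-Aid" and asks "Was the controversy new to you". The other seven rows go to both arms. The tenth knowledge item offers two views of the usefulness of organised screening: that doctors and researchers fully accept it, or "Questioned by some doctors and researchers".

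Section 7 lists the follow-up measures differently: knowledge, attitude, intention, satisfaction, decisional conflict. It then refers to Appendix 3 for the questionnaires themselves.

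**The concern.** The row takes it for granted that a controversy exists. A decision-aid woman reads it shortly before being asked whether the usefulness of screening is disputed; a control woman does not. In the printed form, two of the three components of the endpoint (intention and knowledge) are therefore collected after a prompt that only one arm receives.

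This is separate from the difference in what the arms were taught. Learning about the controversy from the decision aid is a legitimate intervention effect. A reminder inside the outcome questionnaire is not. The follow-up comes 7 to 10 days after randomisation, and section 4.1 lets women stop reading whenever they feel ready, so some decision-aid women may have missed or forgotten this content. Correct answers that they give because of the row would be counted as an effect of the decision aid. The protocol gives no reason for the order and no safeguard against the prompt.

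**Working it through.** **Design figures first.** Section 9.1.3 gives 50% in one group, a 10-point difference, 80% power and two-sided 5%.
- Without continuity correction, for 50% v 60%: n = [1.960·√(2·0.55·0.45) + 0.842·√(0.25 + 0.24)]² / 0.10² = 388 per arm (776 in all).
- With continuity correction: n′ = (n/4)·[1 + √(1 + 4/(n·0.10))]² = 408 per arm, or 816. This matches the plan.
- Invitations: 816 / (0.15 × 2/3) = 8160, as stated.

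The point concerns question order, so these figures only fix the yardstick: 408 per arm and a 10-point target.

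**Which answer is keyed.** No answer key is printed. That the disputed option is the correct one is inferred from the decision-aid text in section 14.2, which presents disagreement among experts.

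**Which components the row can reach.** Follow-up attitude precedes it and is unaffected in the printed order. Intention and knowledge follow it.

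**Knowledge.** Let X be the number correct among the other 12 items, q the chance of answering the cued item correctly, and d the rise in q caused by the row.
- P(adequate) = P(X ≥ 8) + q·P(X = 7)
- Gain in adequate knowledge = d·P(X = 7)
- Gain in informed choice = C·d·P(X = 7), where C is the share with consistent attitude and intention

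The documents give no item-level rates, so these inputs are assumptions: independent items with a common chance p of 60–80%, d of 10–30 points, C of 75–80% and unrelated to knowledge. P(X = 7) = 792·p⁷·(1−p)⁵.

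| p | P(X = 7) | Adequate knowledge, d = 10 / 20 / 30 (points) | Informed choice, d = 10, C = 75% | Informed choice, d = 30, C = 80% |
|---|---|---|---|---|
| 0.60 | 0.227 | 2.3 / 4.5 / 6.8 | 1.7 | 5.4 |
| 0.70 | 0.158 | 1.6 / 3.2 / 4.8 | 1.2 | 3.8 |
| 0.75 | 0.103 | 1.0 / 2.1 / 3.1 | 0.8 | 2.5 |
| 0.80 | 0.053 | 0.5 / 1.1 / 1.6 | 0.4 | 1.3 |

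**Ceiling on the cue.** d cannot exceed the share who would otherwise be wrong. If 90% of decision-aid women would be right without the row, d ≤ 10 points. At C = 75% the gain is then at most 0.10 × 0.053 × 0.75 = 0.4 points (p = 0.80) to 0.10 × 0.227 × 0.75 = 1.7 points (p = 0.60).

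**Intention.** The endpoint rewards agreement between attitude and intention, and only the two most favourable intention answers count as positive. Suppose the row moves a woman from likely to unsure, and unsure is treated as not positive. With attitude at 24 or more she becomes inconsistent; below 24 she becomes consistent. The net sign cannot be derived, so the table holds C fixed.

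**Effect on the test.** With 408 per arm, 50% in the control arm, no true effect and an uncorrected chi-square test (normal approximation), a pure bias of 1, 2, 3 or 5 points moves the two-sided rejection rate from 5% to about 5.9%, 8.8%, 13.7% or 29.8%.

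**The case against.** The strongest reply is that the row adds little. Disagreement among scientists is core content of the decision aid (section 4.1), its home page already announces it (section 14.2), and both arms met the same knowledge item at baseline. Only decision-aid women who would still answer wrongly after all that can gain, and only one of 13 items is directly touched. The row also does not say who disagrees or about what. This stands, and it is why the lower part of the range is more plausible than the upper.

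A reader might infer that the bias can never be examined. The documents do not support that. The end-of-session intention answer is collected before the follow-up form, and knowledge can be rescored in both arms without the cued item. These are only partial checks: rescoring also discards genuine learning on that item, and the earlier intention answer belongs to a different time point from the follow-up attitude score.

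A reader might also infer that the row pushes intention in favour of the decision aid. Nothing in the endpoint definition fixes that direction.

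Finally, section 7 lists the primary-endpoint blocks before satisfaction, and no section says that the platform keeps the printed order of Appendix 3. This is a real uncertainty. It does not remove the problem, because section 7 itself refers to Appendix 3 for the forms, and that is where the row precedes intention and knowledge.

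**Conclusion.** The point holds for the form as printed. An item given to one arm only precedes two of the three components of the primary endpoint and can cue one scored knowledge answer. Any bias in knowledge favours the decision aid. Attitude is not reached, and the direction for intention is unknown.

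The assumed ranges give about 0.4 to 5.4 points of informed choice against the 10-point target, and at most about 0.4 to 1.7 points if 90% of decision-aid women would already answer correctly. A small effect is the likelier case. Every input to these figures is assumed, and the keyed answer is inferred. A reader might conclude that the row could account for most of a positive result. The documents do not support that: the upper end needs a 30-point cue on a topic that the intervention itself teaches. The change is still worth making, because it removes a bias between arms at almost no cost.

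**What to change.** In Appendix 3, ask attitude, intention and knowledge before the satisfaction and SURE blocks in both arms, which agrees with the list in section 7. At minimum, move the decision-aid-only row to the last screen, after knowledge. State in the protocol the order that the platform enforces and whether women can go back to change answers, and confirm the order actually used.

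The cost is re-ordering web screens. It adds no item, participant or visit, and 816 is unchanged.

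If data are already collected, add a sensitivity analysis of informed choice that omits this item in both arms and uses the end-of-session intention answer. Fix the 12-item threshold in advance: 7 of 12 (58.3%) is nearer to the planned 8 of 13 (61.5%) than 8 of 12 (66.7%), and both can be reported. Present it as a partial check, for the reasons given above.
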